#### **AMENDMENTS**

MATIS version 4.0 dated 2nd November 2022

IRAS: 282552 Page **5** of **57** 

The following amendments and/or administrative changes have been made to this protocol since the implementation of the first approved version:

Amendment Number	Date of Amendment	Protocol Version Number	Type of Amendment	Summary of Amendment
1	14.08.2020	1.8	Substantial Amendment	The opening site will be Imperial College Healthcare NHS Trust in the United Kingdom. Additional UK based sites for the trial will include Hillingdon, Royal Free Hospital, Northwick Park and Chelsea and Westminster added according to trial progress. 171 (57 per arm) patients with COVID-19 pneumonia will be recruited to Stage 1, if the trial progresses to Stage 2 an additional maximum of 285 (95 per arm) will be recruited, resulting in a potential sample size of 456 if three trial arms continue for the whole trial (152 per arm). These numbers have been chosen to provide a power of 90% with a maximum 5% chance of an intervention arm being recommended when it provides no improvement over control (5% one-sided family-wise error rate).
2	29.10.2020	1.9	Substantial Amendment	Additional UK sites Leeds and Leicester. Inclusion criteria: CRP now less than or equal to 30 mg/L. Exclusion criteria: removed end stage renal failure, clarified patients on home NIV/CPAP now eligible. Dialysis patients randomised to Ruxolitinib (RUX), will receive only 20mg on dialysis days Week 1, then 10mg on dialysis days Week 2. Pharmacokinetics will be assessed at Baseline, before each dialysis and Day 28. RUX dose for these patients will be assessed after 10 dialysis patients complete Day 14. Research samples will be processed and analysed at Immunology of Infection lab at Imperial College London, St Mary's Campus. Added location of research lab. Updated PIS. Updated early discharge. Trial Team and oversight committees updated. Updated unblinding.
3	24/02/2021	2.0	Non- Substantial	Correcting the name of sites from Northwick Park Hospital to London North West University
			Amendment	Healthcare NHS Trust (Northwick Park Hospital and Ealing Hospital)

IRAS: 282552 Page **6** of **57** 

2	31/03/2021	2.1	Non- Substantial Amendment	Addition of UK site: Sheffield Teaching Hospitals NHS Foundation Trust
3	04/05/20221	2.2	Substantial Amendment	Secondary objective added, to determine the efficacy of RUX or FOS to reduce the level of serum creatinine. Clarification of exclusion criteria, requiring CPAP or high flow nasal oxygen at any point 'after hospital admission' and before baseline not due to a pre-existing condition (e.g. obstructive sleep apnoea). Under Serious Adverse Events, added section 8.3 on Severity Grading. Minor document changes: date of last amendment added, clarified abbreviations for ADL and SAE, updated table of contents to reflect addition of 8.3 SAE grading. Under Schedule of Events in section 9.2, specified labs to be taken at baseline, Days 1, 7, 14 and 28: Coagulation, Chemistry, Ferritin, Troponin, Procalcitonin; added abbreviation for full blood count (FBC); changed follow-up visit windows from +/-1 day to +/-3 days for Days 7, 14 and 28; changed to +1 day for Day 1 and added -2 days for Day 0. Addition of research samples to be taken on day 14 and patient information sheet updated to reflect this change. Under consent in section 12.3, specification of who can take consent to any competent health care professional as delegated by the CI including doctor, nurse or research practitioner.
5	18/05/2022	3.0	Substantial Amendment	Addition of long term follow up sub-study assessing the impact of inflammatory signal inhibitors on the development of PACS. Removal of nasosorption biomarkers at baseline, day 14, day 28 and exploratory endpoints.
6	26/10/2022	4.0	Substantial Amendment	Created a new telephone information and consent process for the long term follow up substudy

IRAS: 282552 Page **7** of **57** 

[figure not shown]

# **ABBREVIATIONS**

ADL	Activities of Daily Living
AE	Adverse Event
ALT	Alanine Aminotransferase
ANC	Absolute Neutrophil Count
ARDS	Adult Respiratory Distress Syndrome
AST	Aspartate Aminotransferase
βhCG	β human chorionic gonadotropin
BP	Blood Pressure
CCO	Central Coordinating Office
CLR	C-type lectin receptors
CPAP	Continuous positive airway pressure
CRF	Case Report Form
CRP	C-Reactive Protein
CXR	Chest X-Ray
DNA	Deoxyribonucleic Acid
FOS	Fostamatinib
ECMO	Extracoporeal membrane oxygenation
EDTA	Ethylene Diamine Tetra-acetic Acid
EoS	End of Study
eGFR	Estimated Glomerula Filtration Rate
FBC	Full Blood Count
FcR	Fc receptors
GI	Gastrointestinal
Hb	Haemoglobin
ICH GCP	International Conference on Harmonisation of Good Clinical Practice
ICL	Imperial College London
ITT	Intention to treat
JAK	Janus kinase
LCC	Local Coordinating Centre
LDH	Lactate dehydrogenase
LFTs	Liver Function Tests
LC	Lymphocyte Count
MSU	Mid-Stream Urine
PACs	Post-acute COVID-19 syndrome
PCR	Polymerase chain reaction
PI	Principal Investigator
PIS-ICF	Patient Information Sheet-Informed Consent Forms
PT	Prothrombin time
QA	Quality assurance
QC	Quality control
R&D	Research and Development
RNA	Ribonucleic acid
RR	Risk Ratio
RRT	Renal Replacement Therapy

IRAS: 282552 Page **8** of **57** 

[figure not shown]
RUX	Ruxolitinib
SAE	Serious Adverse Event
SAR	Serious Adverse Reaction
SOC	Standard of care
STAT	Signal transducer and activator of transcription proteins
TMG	Trial Management Group
TSC	Trial Steering Committee
USS	Ultrasound Scan
VTE	Venous Thromboembolism
WCC	White Cell Count
WHO	World Health Organisation

IRAS: 282552 Page **9** of **57** 

[figure not shown]

# **SYNOPSIS**

TITLE	Randomised multi-arm trial of ruxolitinib (RUX) and fostamatinib (FOS) for COVID-19 pneumonia		
AIM	To evaluate efficacy of RUX and FOS compared to standard of care (SOC) in the treatment of COVID-19 pneumonia		
PRIMARY OBJECTIVE	To determine the efficacy of RUX and FOS compared to standard of care (SOC) to reduce the proportion of hospitalised patients progressing from mild or moderate to severe COVID-19 pneumonia		
SECONDARY OBJECTIVES	
 
Determine the efficacy of RUX or FOS to reduce mortality
 
Determine the efficacy of RUX or FOS to reduce the need for invasive ventilation or ECMO
 
Determine the efficacy of RUX or FOS to reduce the need for non-invasive ventilation
 
Determine the efficacy of RUX or FOS to reduce the proportion of patients suffering significant oxygen desaturation
 
Determine the efficacy of RUX or FOS to reduce the need for renal replacement therapy
 
Determine the efficacy of RUX and FOS to reduce the incidence of venous thromboembolism COVID-19 pneumonia
 
Determine the efficacy of RUX and FOS to reduce the severity on COVID-19 pneumonia [graded by a modified WHO Ordinal Scale]
 
Determine the efficacy of RUX or FOS to reduce the level of inflammatory biomarkers
 
Determine the efficacy of RUX or FOS to reduce blood ferritin, CRP, LDH, and D-dimer
 
Determine the efficacy of RUX or FOS to reduce the level of serum creatinine
 
Determine the efficacy of RUX or FOS to reduce duration of hospital admission
 
Evaluate the safety of RUX and FOS for COVID-19 pneumonia
 
Determine the impact of RUX or FOS to reduce the development of the post-acute COVID-19 syndrome in patients who presented with mild-moderate COVID-19 pneumonia
 
Assess impact of signal inhibitors (RUX or FOS) on health related quality of life at 6, 12 and 18 months post COVID-19
 
		
DESIGN	Multi-site, Two stage, open label, randomized (1:1:1) controlled trial		
STUDY DURATION	Treatment is for 14 day from baseline. Patients will receive follow-up assessment at 7, 14 and 28 days after the first study dose.  Screen Period: up to 7 days		
	Treatment Period: 14 days		
	1.000.00.1.00.2.00.0		

MATIS version 4.0 dated 2nd November 2022

IRAS: 282552 Page **14** of **57** 

[figure not shown]

	T
	Follow-up period: Day 14 to 28
	Follow-up period of sub-study: Up to 24 months
SAMPLE SIZE	171 in Stage 1 (57 per arm) and up to an additional 285 in Stage 2 (additional 95 per included arm), to allow for 5% dropout. Patients with mild or moderate COVID-19 pneumonia will be recruited. Patients will be enrolled into RUX, FOS or SOC groups, as shown in the flow chart.
STUDY SITES	The opening site will be Imperial College Healthcare NHS Trust in the United Kingdom. Additional UK based sites for the trial will include Reading, London North West University Healthcare NHS Trust (Northwick Park Hospital and Ealing Hospital, Leeds and Sheffield Teaching Hospitals NHS Foundation Trust.
INCLUSION CRITERIA	
 
Patients age ≥ 18 years at screening
 
Patients with mild or moderate C19 pneumonia, defined as Grade 3 or 4 severity by the WHO COVID-19 Ordinal Scale
 
Patients meeting criteria:         
 
Hospitalization AND
 
SARS-CoV2 infection (clinically suspected* or laboratory confirmed) AND
 
Radiological change consistent with COVID-19 disease
 
 
 
CRP ≥ 30mg/L at any time point
 
Informed consent from patient or personal or professional representative
 
Agreement to abstain from sexual intercourse or use contraception that is >99% effective for all participants of childbearing potential for 42 days after the last dose of study drug. For male participants, agreement to abstain from sperm donation for 42 days after the last dose of study drug.
 
Non-English speakers will be able to join the study. If patients are unable to understand verbal or written information in English - hospital translation services will be requested at the participating site for the participant where possible.
 

	Patients normally on non-invasive ventilation such as continuous positive airway pressure (CPAP) at home are eligible
EXCLUSION CRITERIA	
 
Requiring either invasive or non-invasive ventilation including CPAP or high flow nasal oxygen at any point after hospital admission and before baseline not due to a pre-existing condition (e.g. obstructive sleep apnoea)
 
Grade ≥ 5 severity on the modified WHO COVID-19 Ordinal Scale, viz. O2 saturation < 90% on ≥ 60% inspired oxygen at baseline; non-invasive
 

	
 
Ventilation; or invasive mechanical ventilation
 
In the opinion of the investigator, progression to death is inevitable within the next 24 hours, irrespective of the provision of therapy
 
Known severe allergic reactions to the investigational agents
 

MATIS version 4.0 dated 2nd November 2022

IRAS: 282552 Page **15** of **57** 

	
 
Child Pugh B or C grade hepatic dysfunction
 
Use of drugs within the preceding 14 days that are known to interact with any study treatment (FOS or RUX), as listed in the Summary of Product Characteristics
 
Pregnant or breast feeding
 
Any medical condition or concomitant medication that in the opinion of the investigator would compromise subjects' safety or compliance with study procedures.
 
Any medical condition which in the opinion of the principal investigator would compromise the scientific integrity of the study
 
		
MAIN STUDY PROCEDURES	Specific assessments occur at:		
	Day 14: death, ventilation status, oxygenation status, renal status		
	Day 28: death, ventilation status, oxygenation status, renal status		
PRIMARY ENDPOINTS	
 
Pairwise comparison of the proportion of patients diagnosed with severe COVID-19 pneumonia within 14 days.
 
Severe COVID-19 pneumonia is defined by a modified WHO COVID-19 Ordinal Score ≥ 5, comprising the following indicators of disease severity:         
 
Death OR
 
Requirement for invasive ventilation OR
 
Requirement for non-invasive ventilation including CPAP or high flow oxygen OR
 
O₂ saturation < 90% on ≥60% inspired oxygen
 
 
 
		
SECONDARY ENDPOINTS	
 
Pairwise comparison of the proportion, median or odds ratio of each of the parameters below at 14 and 28 days between RUX or FOS versus SOC:         
 
Mortality
 
Invasive ventilation or ECMO
 
 
 
Non-invasive ventilation including CPAP or high flow nasal oxygen
 
Renal replacement therapy
 
Venous thromboembolism

		
	
 
Mortality at 3, 6, 12 & 18 months.
 
Venous thromboembolism rate at 3, 6, 12 and 18 months
 
Renal replacement therapy at 3, 6, 12 and 18 months
 
		

MATIS version 4.0 dated 2nd November 2022

IRAS: 282552 Page **16** of **57** 

	
 
Number of re-admissions within 12 months
 
Occurrence of lung fibrosis
 
Number of re-infections of COVID-19
 
Additional co-morbidities developed during long-term follow up period
 

EXPLORATORY ENDPOINTS	
 
Biomarkers of disease including plasma, PBMC and RNA/DNA changes
 
Changes in health related quality of life
 

	Further secondary and exploratory objectives are not the focus of this study but maybe adopted using routine healthcare records (e.g. NHS Digital or equivalent international databases) and relevant research studies (e.g. UK Biobank or equivalent international resources). This will allow subsidiary analyses of the effect of the study treatments on particular non-fatal events (e.g. ascertained through linkage to Hospital Episode Statistics), the influence of pre-existing major co-morbidity (e.g. chronic heart disease and use of immunosuppressive drugs) and longer-term outcomes (e.g. 6 month survival) as well as in particular sub-categories of patient (e.g. by genotype).

[figure not shown]
#### 1 INTRODUCTION

#### 1.1 BACKGROUND

COVID-19 pneumonia is characterised by respiratory and multi-organ failure in the context of marked systemic inflammation. It is caused by Severe Acute Respiratory Syndrome Coronavirus 2 (SARSCoV2) infection. The hallmark of severe disease is hypoxia and a radiological pattern of acute lung injury that shares features with Acute Respiratory Distress Syndrome (ARDS). Early features of COVID-19 result from host viral response and typically include symptoms such as fever and dry cough. Later features, typically occurring beyond 7 days, are characterised by marked and progressive systemic inflammation, identified by elevations in a plethora of inflammatory molecules such as C-reactive protein, ferritin and IL6. In a subset of patients, hyperinflammatory responses drive acute lung injury and may result in catastrophic multi-organ failure and death (Huang et al., 2020).

Figure 1. Classification of COVID-19 Disease States and Potential Therapeutic Targets

IRAS: 282552 Page **17** of **57** 

(Siddigi & Mehra, 2020)

The aetiology of COVID-19 induced ARDS is incompletely understood but appears to be associated with lung inflammation effected by a monocytic and neutrophilic infiltration, elevated cytokine levels and tissue damage (Siddiqi & Mehra, 2020). Elevations in circulating inflammatory molecules are associated with poor prognosis. In particular, the COVID-19 hyperinflammatory response syndrome is associated thrombotic complications which are postulated to drive cardiac dysfunction and microvascular thrombi, suggested by elevations in troponin and D-dimer, respectively (Ruan et al., 2020). Similar hyperinflammatory responses are also seen in macrophage activation syndromes such as haemophagocytic lymphohistiocytosis, or in the cytokine release syndrome associated with chimeric antigen receptor T cell therapy (Singanayagam et al., 2018). Further, preliminary data from China and Italy have shown immediate resolution of symptoms using anti-IL6 therapy and JAK/STAT inhibitors in patients with severe disease (Richardson et al., 2020; Wu & Yang, 2020). There may be an early window of opportunity to treat the COVID-19 hyperinflammatory syndrome before acute lung injury leads to organ failure.

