**Table 7. Schedule of events** 

	Screening	Baseline				Last visit
Study Day	-6 to 0	0	1 *	7 #	14#	28#
Time window		- 2 days	+ 1 day	± 3 days	± 3 days	± 3 days
Informed consent	х					
Inclusion/Exclusion criteria	х	Х				
Demographic data	х					
Medical history including major comorbidities	х					
Physical exam	х					
COVID-19 diagnosis, duration and severity	х					
Pregnancy test	х					
Vital signs	х	Х	Х	Х	Х	Х
NEWS score	х	Х	Х	Х	х	Х
Inflammatory markers (CRP, D-dimer, LDH, ferritin, full blood count)		х	Х	х	х	Х
PK levels*					х	Х
Full blood count ¶ (FBC)		Daily while on CYP3A4 inhibitor				
Coagulation, Chemistry, Ferritin, Troponin, Procalcitonin	х	х	x	x	х	х
FiO 2	х	Х	Х	х	х	Х
SpO₂ and/or PaO₂	х	Х	х	х	х	Х
Randomisation		Х				
Weight and Estimated height		Х				
Safety monitoring of liver and renal function	х	Х	Х	Х	х	Х
Length of stay						
Serious Adverse Events	х	Х	Х	х	х	х
Concomitant medications	Х	Х	Х	х	Х	Х
Serum		х		х	Х	х
Plasma		Х		х	Х	Х
RNA in PAXgene tube		Х		Х	Х	Х
PBMC		x		х	х	Х

<sup>+ data that is routinely collected for clinical purposes will be recorded and a visit is not required

<sup># in the event that the patient recovers from COVID19 and is discharged, these visits will not be mandated. Instead a visit should occur on the date of discharge. Where possible, patients will be contacted by telephone at day 7, 14 and 28 and invited to attend for blood tests to monitor resolution of illness.

\*Ruxolitinib dose for these patients will be assessed after 10 dialysis patients complete Day 14 through pharmacokinetics (PK) levels which will be assessed.

<sup>¶For patients randomized to ruxolitinib and prescribed a strong CYP3A4 inhibitor or dual CYP3A4/CYP2C9 inhibitor. Please refer to Section 7.8 for details.

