1.5.1 Sample size for formal interim analysis (Stage 1)

Current rate of severe pneumonia in the standard of care is 50%. In the case that an experimental arm reduces this to 30% (relative risk, RR, 0.6), then the design provides a 92% chance (one-sided alpha of 0.25, equivalent to stopping for futility if the one-sided p-value is >0.25) of it being recommended to continue to stage 2.

The design recommends stopping an intervention arm at stage 1 if the one-sided p-value is >0.25 but this is a non-binding rule (i.e. the overall power is calculated assuming this rule is always followed and the family-wise error rate (FWER) is calculated assuming it is not followed). The actual FWER will be lower if the rule is always followed).

Recruitment to the trial will continue during this interim analysis stage.

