1.5.2 Sample size for full trial (Stage 2)

If the trial is recommended to continue at Stage 2 based on DMC interim review, the full trial will need to recruit an additional 95 for each arm that continues (152 per arm in total; 456 to the complete trial). This will provide 90% power to detect a change of RR of 0.6 (50% to 30%), with one-sided alpha of 0.027 (chosen to give a 5% FWER) and has been inflated by 5% for missing outcome data. Here the power is the chance of an effective treatment passing stage 1 and being recommended after stage 2.

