The stage two primary analysis will consist of fitting one binomial regression model regardless of whether one or two experimental treatments progress from stage one. Specifically a generalized linear model with WHO COVID-19 status (<5 or \ge 5) as the outcome and treatment group, baseline WHO COVID-19 score (3 or 4), age (<65 or \ge 65), receipt of known effective treatments dexamethasone and/or tociluzimab, prior vaccination against COVID-19 (y/n) and receipt of paxlovid and/or molnupiravir at the time of or prior to randomisation into MATIS as covariates will be fitted. Effective treatments will be included as separate covariates in the primary analysis model. Given the anticipated small number of sites in this study, site will also be included in the model as a fixed effect. In the event that all participants are on one of the effective treatments that covariate will be removed from the model.

If including site as a fixed effect results in unstable model estimates e.g. if there are a number of sites with very few randomisations we will exclude site from the model and we will only adjust for baseline WHO COVID score, age group, receipt of known effective treatments dexamethasone and/or tociluzimab, prior vaccination against COVID-19, and receipt of paxlovid and/or molnupiravir.⁶ We will also consider not adjusting for paxlovid and/or molnupiravir if the number of participants receiving these are low. If after removing sites and treatments the model is not stable due to event rate:covariate ratio we will adjust for all covariates using a propensity score approach.

The model will be fitted with a binomial distribution and logit link function and the treatment effect will be reported as an odds ratio with corresponding 95% confidence interval and p-values. P-values will be one-sided and judged at the 0.027 level. Therefore, a two-sided p-value < 0.054 will be used to indicate a significant treatment effect.

The stage two model to be fitted to estimate the treatment effects will be:

$$logit(\pi_{ij}) = \beta_{0} + \beta_{1}RUX_{ij} + \beta_{2}FOS_{ij} + \beta_{3}WHO_{ij}^{0} + \beta_{4}AGE_{ij}^{0} + \beta_{5}DEX_{ij}^{0} + \beta_{6}TOC_{ij}^{0} + \beta_{7}VAC_{ij}^{0} + \beta_{8}PAX_{ij}^{0} + \beta_{9}MOL_{ij}^{0} + \beta_{10}SITE_{1} + \beta_{11}SITE_{2} + \cdots + \beta_{12}SITE_{i-1}$$

 RUX_{ij} : dummy variable for treatment ($RUX_{ij} = 0$ or 1) for participant i in jth site

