3.2.5 Continuous laboratory values

For inflammatory markers of CRP, LDH, ferritin, D-dimer and serum creatinine levels a linear mixed effect model will be used to estimate the mean difference in values between intervention arms (RUX and FOS) and SOC at each follow-up visit (day 1, day 7 and day 14). Participants will be included as a random intercept with fixed effects for time, time-by-treatment arm interaction and baseline values. Stratification variables age and site, plus receipt of known effective treatments dexamethasone and/or tociluzimab, prior vaccination against COVID-19, and receipt of paxlovid and/or molnupiravir at the time of or prior to randomisation into MATIS will also be included as fixed effects. Baseline adjusted treatment group differences with 95% confidence intervals will be presented for each time-point.

For example for CRP the model to be fitted to estimate the treatment effect at each visit up to day 14 will be:

$$\begin{split} Y_{ijt} = \ \beta_0 + \ \beta_1 R U X_{ij} + \ \beta_2 F O S_{ij} + \ \beta_3 C R P_{ij}^0 + \ \beta_4 A G E_{ij}^0 + \ \beta_5 D E X_{ij}^0 \\ + \ \beta_6 T O C_{ij}^0 + \ \beta_7 V A C_{ij}^0 + \ \beta_8 P A X_{ij}^0 + \ \beta_9 M O L_{ij}^0 \ \beta_{10} time_7 \\ + \ \beta_{11} time_{14} + \ \beta_{12} R U X_{ij} * time_7 + \ \beta_{13} R U X_{ij} * time_{14} \\ + \ \beta_{14} F O S_{ij} * time_7 + \ \beta_{15} F O S_{ij} * time_{14} + \ \beta_{16} S I T E_1 \\ + \ \beta_{17} S I T E_2 + \dots + \ \beta_{18} S I T E_{j-1} + b_{1,i} + e_{it} \end{split}$$

for

t = 1 to 3 time points (day 1, 7 and 14), i = 1 to 30 participants

 RUX_{ij} : dummy variable for treatment ($RUX_{ij} = 0 \text{ or } 1$) for participant i

 FOX_{ij} : dummy variable for treatment ($FOS_{ij} = 0 \text{ or } 1$) for participant i

 CRP_{ij}^{0} : baseline CRP value for participant i

 DEX_{ij}^0 : dummy variable for receipt of dexamethasone at the time of or prior to randomisation (includes day of randomisation or one day post randomisation) ($DEX_{ij} = 0 \text{ or } 1$) for participant i TOC_{ij}^0 : dummy variable for receipt of tociluzimab at the time of or prior to randomisation (includes day of randomisation or one day post randomisation) ($TOC_{ij} = 0 \text{ or } 1$) for participant i VAC_{ij}^0 : dummy variable for prior vaccination against COVID-19 at the time of or prior to randomisation (includes day of randomisation or one day post randomisation) ($VAC_{ij} = 0 \text{ or } 1$) for participant i

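### Baseline CRP is left out of the stage 2 primary model: a cheap efficiency gain forgone, not an error, since the stated 90% power is met without it

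*Protocol*

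**What the plan says.** Protocol 1.1 describes progressive systemic inflammation, gives CRP, ferritin and IL6 as examples of the molecules that rise, and then states: "Elevations in circulating inflammatory molecules are associated with poor prognosis". It gives no effect size.

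CRP is used at several points in the trial:
- Entry requires at least 30 mg/L at any time point (protocol 5.2).
- It was the marker for the dose check (protocol 7.1; SAP 1.9).
- A value above 200 mg/L defines a subgroup for the primary outcome (protocol 4.2; SAP 3.1.6).
- Protocol Table 7 marks the row "Inflammatory markers (CRP, D-dimer, LDH, ferritin, full blood count" at Day 0.
- The laboratory model for CRP in SAP 3.2.5 adjusts for the "baseline CRP value for participant i".

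The stage 2 primary model in SAP 3.1.3 adjusts for baseline WHO score, age group and site, together with "receipt of known effective treatments dexamethasone and/or tociluzimab, prior vaccination against COVID-19 (y/n) and receipt of paxlovid and/or molnupiravir". Protocol 4.2 lists the arms, baseline WHO score, co-enrolment at baseline, site and age. The stage 1 propensity score in SAP 3.1.2 uses WHO score, age, dexamethasone and tocilizumab. None of the three includes CRP. Randomisation is stratified by age and site only (protocol 6.2; SAP 1.6).

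**The concern.** A pre-specified baseline covariate that predicts the outcome makes the treatment comparison in a logistic model more efficient. By the plan's own account CRP belongs to a prognostic class of markers. It is scheduled for collection anyway, and it reflects the inflammation that both drugs are meant to reduce. Neither the randomisation nor the primary model takes direct account of a chance imbalance in it between arms.

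At stake is some precision for the primary comparison, obtainable without new data collection or any change to treatment.

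**Working it through.** **Inputs from the documents.** Rates are 50% and 30%; 57 per arm at stage 1 and 152 per arm in total; 5% missing outcomes (SAP 1.5 to 1.5.2). The stage 1 threshold is "one-sided alpha of 0.25, equivalent to stopping for futility if the one-sided p-value is >0.25" and the final one-sided threshold is 0.027. Power is joint: "Here the power is the chance of an effective treatment passing stage 1 and being recommended after stage 2". The sample size is for a Bernoulli outcome, with no credit for covariates mentioned (SAP 1.5).

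**Step 1: the plan's own figures, with no covariates.** Evaluable patients: 57 × 0.95 ≈ 54 and 152 × 0.95 ≈ 144 per arm. With mean rate 0.40, SE0 = √(2 × 0.40 × 0.60 / n), SE1 = √((0.50 × 0.50 + 0.30 × 0.70) / n), and power = Φ((0.20 − z × SE0) / SE1).
- Stage 1, n = 54: (0.20 − 0.674 × 0.0943) / 0.0923 = 1.48, giving 93.0% (stated: 92%).
- Final test alone, n = 144: (0.20 − 1.927 × 0.0577) / 0.0565 = 1.57, giving 94.2%.
- Both together, bivariate normal with correlation √(54/144) = 0.61: 89.4%. With 57 and 152 evaluable it is 90.8% (stated: 90%).
- Family-wise error for two arms sharing a control at 0.027 (correlation 0.5): 4.9%, within the 5% limit.

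The stated power is therefore reached without a CRP term.

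**Step 2: what a CRP term could add.** This uses 8,000 simulated trials per scenario, one active arm against control, 54 then 144 per arm, logistic Wald tests, and overall rates held at 50% and 30%. The strength of CRP is an assumption: the odds ratio per SD of a standardised CRP covariate (log CRP in the proposed model), read as what remains after the covariates already in the model. Those covariates were not simulated. Entries are joint power.

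| Assumed OR per SD | No CRP term | CRP at both looks | CRP at final test only |
|---|---|---|---|
| 1.0 | 89.0% | 88.9% | 88.9% |
| 1.3 | 88.9% | 89.5% | 89.0% |
| 1.5 | 88.9% | 89.9% | 89.3% |
| 2.0 | 88.8% | 91.5% | 90.3% |
| 2.5 | 88.9% | 92.8% | 90.6% |
| 3.0 | 89.3% | 93.7% | 91.4% |

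Monte Carlo error is about 0.3 points, and less for differences within a row. The last column pairs the unadjusted stage 1 decision with the adjusted final test in the same simulated trials. It is the relevant column if only the stage 2 model changes.

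**Step 3: a lower event rate.** Protocol 1.3 puts deterioration needing ventilatory support at around 30%, a narrower event than the primary outcome. At 30% versus 18% (the same relative risk of 0.6), with CRP at both looks, joint power goes from 60.8% to 62.0% (OR 1.5), 61.2% to 64.3% (2.0) and 61.5% to 68.5% (3.0). Monte Carlo error is about 0.5 points.

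**Step 4: room in the model.** Expected events among evaluable patients: 144 × (0.50 + 0.30 + 0.30) ≈ 158. Parameters now: 2 arms + 7 covariates + 5 site terms (six sites assumed) = 14. Events per parameter fall from 158/14 = 11.3 to 158/15 = 10.5 with CRP. At 30/18/18% there are 144 × 0.66 ≈ 95 events, and the ratio falls from 6.8 to 6.3.

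**The case against.** **The planned power does not need CRP.** This stands. A reader might infer that the omission erodes the stated 90%, but step 1 shows that it does not. A reader might also infer that the planned odds ratio is biased towards no effect. The documents do not support that either: odds ratios with and without CRP are different quantities. In the simulations, overall rates of 50% and 30% give an odds ratio of 0.43 without CRP and 0.39 given CRP when CRP has an odds ratio of 2.0 per SD. The planned difference in proportions (SAP 3.1.3) is not affected in this way, and the test's error rate already allows for chance imbalance.

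**The strength of CRP is unknown.** This stands. The background statement is qualitative and concerns a class of markers. Overlap with WHO score and dexamethasone, or selection on CRP at entry, could shrink what remains. Because the entry criterion allows a qualifying value at any time, baseline CRP need not be cut off at 30 mg/L.

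**The SAP is already limiting covariates.** This stands in part. SAP 3.1.3 foresees instability and sets an order of retreat: drop site, consider dropping the antivirals, then use a propensity score. It would therefore be wrong to call the omission wholly without reason. But one continuous term barely moves the ratio in step 4, and that order of retreat can stay as it is.

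**Why CRP and not D-dimer, LDH or ferritin?** These are scheduled at baseline too, and the background statement does not rank them. CRP has the better claim because the trial already uses it for entry, for the dose check and for a subgroup.

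**Unblinded data have been seen.** SAP 1.9 records that the monitoring committee and the chief investigator reviewed unblinded efficacy data by 29 January 2021, with CRP by arm as planned evidence. This does not rule out the change, but the reason for it has to be documented.

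**Conclusion.** The point holds as an optional improvement in efficiency, not as a fault in the design or the test. With CRP at both looks, joint power at the design effect rises by about 0.5 to 1 point for a residual odds ratio per SD of 1.3 to 1.5, about 3 points at 2.0 and about 4.5 points at 3.0. If only the final analysis changes, the gains are about 0.1 to 0.4, 1.5 and 2 points. With no residual prognostic value the cost is about 0.1 point, within simulation error.

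All these sizes rest on an assumed strength for CRP that the documents do not supply. Step 3 suggests somewhat more to gain if event rates are lower and CRP is strongly prognostic, but that scenario borrows its control rate from a different event.

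**What to change.** Before final unblinding:
- Add log-transformed baseline CRP, the last value not after randomisation, as one continuous covariate in the SAP 3.1.3 model. Add it also to the 28-day model that reuses it (SAP 3.2.1) and to the imputation model.
- For a missing baseline value, use the SAP's existing mean imputation, on the log scale.
- Keep the existing order of retreat in SAP 3.1.3 if the model is unstable.
- Align the covariate list in protocol 4.2.
- Record that the change was not driven by the unblinded dose-check data.

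If stage 1 has not yet been analysed, the same term could go into the stage 1 propensity score (SAP 3.1.2); the larger gains need it at both looks.

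The cost is wording in two documents, one degree of freedom, and an odds ratio that is conditional on CRP. The planned risk difference keeps its meaning if it is averaged over the trial population. If the team prefers to leave CRP out, a sentence giving the reason would be enough.
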